5.6 Table 6: Treatment Modification for Symptoms of Infusion-Related Reactions

NCI-CTCAE Grade	Modification of Study Drug
Grade 1 – mild Mild transient reaction; infusion interruption not indicated; intervention not indicated.	Decrease the study drug infusion rate by 50% and monitor closely for any worsening. The total infusion time for study drug should not exceed 120 minutes.
Grade 2 – moderate Therapy or infusion interruption indicated but responds promptly to symptomatic treatment (for example, antihistamines, NSAIDs, narcotics, IV fluids); prophylactic medications indicated for ≤ 24 h.	Hold the study drug infusion. Resume infusion at 50% of previous rate once infusion-related reaction has resolved or decreased to \leq Grade 1 in severity, and monitor closely for any worsening.
Grade 3 or Grade 4 – severe or life-threatening Grade 3: Prolonged (for example, not rapidly responsive to symptomatic medication and/or brief interruption of infusion); recurrence of symptoms following initial improvement; hospitalization indicated for clinical sequelae. Grade 4: Life-threatening consequences; urgent intervention indicated.	Stop the study drug infusion immediately and disconnect infusion tubing from the subject. Subjects have to be withdrawn immediately from study drug treatment and must not receive any further study drug treatment.

- Once the avelumab infusion rate has been decreased by 50% or interrupted due to an infusion-related reaction, it must remain decreased for all subsequent infusions.- If the subject has a second infusion-related reaction Grade ≥ 2 on the slower infusion rate, the infusion should be stopped and the subject should be removed from study treatment.- If hypersensitivity reaction occurs, the subject must be treated according to the best available medical practice.	

IV = intravenous; NCI-CTCAE = National Cancer Institute-Common Terminology Criteria for Adverse Event; NSAIDs = nonsteroidal anti-inflammatory drugs.

5.7 Table 7: Management of Immune-Related Adverse Reactions

Since inhibition of PD-L1 stimulates the immune system, immune-related AEs (irAEs) may occur. Treatment of irAEs is mainly dependent upon severity (NCI-CTCAE grade):

- Grade 1 to 2: treat symptomatically or with moderate dose steroids, more frequent monitoring
- Grade 1 to 2 (persistent): manage similar to high grade AE (Grade 3 to 4)
- Grade 3 to 4: treat with high dose corticosteroids

Treatment of gastrointestinal, dermatological, pulmonary, hepatic, endocrine and cardiac irAEs should follow guidelines set forth in the table below.

Gastrointestinal irAEs		
Severity of Diarrhea / Colitis (NCI-CTCAE v4.03)	Management	Follow-up
Grade 1 Diarrhea: < 4 stools/day over baseline Colitis: asymptomatic	Continue avelumab therapy Symptomatic treatment (for example, loperamide)	Close monitoring for worsening symptoms Educate subject to report worsening immediately If worsens: Treat as Grade 2 or 3/4
Grade 2 Diarrhea: 4 to 6 stools per day over baseline; IV fluids indicated < 24 hours; not interfering with ADL Colitis: abdominal pain; blood in stool	Delay avelumab therapy unless systemic steroids needed. If systemic steroids are needed, discontinue avelumab. Symptomatic treatment	If improves to Grade 1: Resume avelumab therapy If persists > 5 to 7 days or recurs: 0.5 to 1.0 mg/kg/day methylprednisolone or equivalent; when symptoms improve to Grade 1, taper steroids over at least 1 month, consider prophylactic antibiotics for opportunistic infections and remove patient from study treatment. If worsens or persists > 3 to 5 days with oral steroids: Treat as Grade 3 to 4
Grade 3 to 4 Diarrhea (Grade 3): ≥ 7 stools per day over baseline; incontinence; IV fluids ≥ 24 hrs.; interfering with ADL	Discontinue avelumab therapy per protocol 1.0 to 2.0 mg/kg/day methylprednisolone IV or equivalent	If improves: Continue steroids until Grade 1, then taper over at least 1 month If persists > 3 to 5 days, or recurs after improvement:

Colitis (Grade 3): severe abdominal pain, medical intervention indicated, peritoneal signs Grade 4: life-threatening, perforation	Add prophylactic antibiotics for opportunistic infections Consider lower endoscopy	Add infliximab 5 mg/kg (if no contraindication), Note: Infliximab should not be used in cases of perforation or sepsis
--	---	--

Dermatological irAEs

Grade of Rash (NCI-CTCAE v4)	Management	Follow-up
Grade 1 to 2 Covering \leq 30% body surface area	Symptomatic therapy (for example, antihistamines, topical steroids) Continue avelumab therapy unless systemic steroids are needed. If systemic steroids are needed, discontinue avelumab.	If persists > 1 to 2 weeks or recurs: Consider skin biopsy Delay avelumab therapy Consider 0.5 to 1.0 mg/kg/day methylprednisolone IV or oral equivalent. Once improving, taper steroids over at least 1 month, consider prophylactic antibiotics for opportunistic infections, and if systemic steroids used discontinue study treatment. If worsens: Treat as Grade 3 to 4
Grade 3 to 4 Covering $>$ 30% body surface area; life threatening consequences	Discontinue avelumab therapy Consider skin biopsy Dermatology consult 1.0 to 2.0 mg/kg/day methylprednisolone IV or IV equivalent	If improves to Grade 1: Taper steroids over at least 1 month and add prophylactic antibiotics for opportunistic infections

Pulmonary irAEs

Grade of Pneumonitis (NCI-CTCAE v4)	Management	Follow-up
Grade 1 Radiographic changes only	Consider delay of avelumab therapy	Re-image at least every 3 weeks

	
Monitor for symptoms every 2 to 3 days
 
Consider Pulmonary and Infectious Disease consults
	
If worsens: Treat as Grade 2 or Grade 3 to 4

Grade 2 Mild to moderate new symptoms
	
Discontinue avelumab therapy
 
Pulmonary and Infectious Disease consults
 
Monitor symptoms daily, consider hospitalization
 
1.0 mg/kg/day methylprednisolone IV or oral equivalent
 
Consider bronchoscopy, lung biopsy
	
Re-image every 1 to 3 days
 
If improves: When symptoms return to near baseline, taper steroids over at least 1 month and consider prophylactic antibiotics.
 
If not improving after 2 weeks or worsening: Treat as Grade 3 to 4

Grade 3 to 4 Severe new symptoms; New / worsening hypoxia; life-threatening
	
Discontinue avelumab therapy
 
Hospitalize
 
Pulmonary and Infectious Disease consults
 
2 to 4 mg/kg/day methylprednisolone IV or IV equivalent
 
Add prophylactic antibiotics for opportunistic infections
 
Consider bronchoscopy, lung biopsy
	
If improves to baseline: Taper steroids over at least 6 weeks
 
If not improving after 48 hours or worsening: Add additional immunosuppression (for example, infliximab, cyclophosphamide, IV immunoglobulin, or mycophenolate mofetil)

Hepatic irAEs		
Grade of Liver Test Elevation (NCI-CTCAE v4)	Management	Follow-up
Grade 1 AST or ALT > ULN to 3.0 x ULN and / or total bilirubin > ULN to 1.5 x ULN	Continue avelumab therapy	Continue liver function monitoring If worsens: Treat as Grade 2 or 3 to 4
Grade 2 AST or ALT > 3.0 to \leq 5 x ULN and / or total bilirubin > 1.5 to \leq 3 x ULN	Delay avelumab therapy. If systemic steroids are required, avelumab therapy will be discontinued. Increase frequency of monitoring to every 3 days	If returns to Baseline: Resume routine monitoring, resume avelumab therapy If elevations persist > 5 to 7 days or worsens: 0.5 to 1 mg/kg/day methylprednisolone or oral equivalent and when LFT returns to grade 1 or baseline, taper steroids over at least 1 month, consider prophylactic antibiotics for opportunistic infections, and discontinue avelumab therapy

Grade 3 to 4 AST or ALT > 5 x ULN and / or total bilirubin > 3 x ULN
	
Discontinue avelumab therapy Increase frequency of monitoring to every 1 to 2 days 1.0 to 2.0 mg/kg/day methylprednisolone IV or IV equivalent Add prophylactic antibiotics for opportunistic infections Consult gastroenterologist Consider obtaining MRI/CT scan of liver and liver biopsy if clinically warranted
	
If returns to Grade 2: Taper steroids over at least 1 month If does not improve in > 3 to 5 days, worsens or rebounds: Add mycophenolate mofetil 1 gram (g) twice daily If no response within an additional 3 to 5 days, consider other immunosuppressants per local guidelines

Endocrine irAEs		
Endocrine Disorder	Management	Follow-up
Asymptomatic TSH abnormality	
Continue avelumab therapy If TSH < 0.5 x LLN, or TSH > 2 x ULN, or consistently out of range in 2 subsequent measurements: include T4 at subsequent cycles as clinically indicated; consider endocrinology consult
	
Symptomatic endocrinopathy	
Evaluate endocrine function Consider pituitary scan Symptomatic with abnormal lab / pituitary scan: Discontinue avelumab therapy 1 to 2 mg/kg/day methylprednisolone IV or by mouth equivalent (with the exception of diabetes mellitus)
	
If improves (with or without hormone replacement): Taper steroids over at least 1 month and consider prophylactic antibiotics for opportunistic infections Subjects with adrenal insufficiency may need to continue steroids with mineralocorticoid component

	
Initiate appropriate hormone therapy
 
No abnormal lab / pituitary MRI scan but symptoms persist: Repeat labs in 1 to 3 weeks / MRI in 1 month
	
Suspicion of adrenal crisis (for example, severe dehydration, hypotension, shock out of proportion to current illness)	
Delay or discontinue avelumab therapy
 
Rule out sepsis
 
Stress dose of IV steroids with mineralocorticoid activity
 
IV fluids
 
Consult endocrinologist
 
If adrenal crisis ruled out, then treat as above for symptomatic endocrinopathy.
	

Cardiac irAEs

Myocarditis	Management	Follow-up
New onset of cardiac signs or symptoms and / or new laboratory cardiac biomarker elevations (e.g. troponin, CK-MB, BNP) or cardiac imaging abnormalities suggestive of myocarditis.	
Withhold avelumab therapy
 
Hospitalize. In the presence of life threatening cardiac decompensation, consider transfer to a facility experienced in advanced heart failure and arrhythmia management.
 
Cardiology consult to establish etiology and rule-out immune-mediated myocarditis.
 
Guideline based supportive treatment as appropriate per cardiology consult.*
 
Consider myocardial biopsy if recommended per cardiology consult.
	
If symptoms improve and immune-mediated etiology is ruled out, restart avelumab therapy.
 
If symptoms do not improve/worsen, viral myocarditis is excluded, and immune-mediated etiology is suspected or confirmed following cardiology consult, manage as immune-mediated myocarditis.

Immune-mediated myocarditis	
Permanently discontinue avelumab.
 
Guideline based supportive treatment as appropriate per cardiology consult.*
	
Once improving, taper steroids over at least 1 month and add prophylactic antibiotics for opportunistic infections.

	Methylprednisolone 1-2 mg/kg/day.	If no improvement or worsening, consider additional immunosuppression (e.g. azathioprine, cyclosporine A)
--	-----------------------------------	---

ADL = activities of daily living; ALT = alanine aminotransferase; AST = aspartate aminotransferase; CT = computed tomography; irAE = immune-related adverse event; IV=intravenous; LFT = liver function test; LLN = lower limit of normal; MRI = magnetic resonance imaging; NCI-CTCAE = National Cancer Institute-Common Terminology Criteria for Adverse Event; T4 = free thyroxine; TSH = thyroid-stimulating hormone; ULN = upper limit of normal. *Local guidelines, or eg. ESC or AHA guidelines. ESC guidelines website: <https://www.escardio.org/Guidelines/Clinical-Practice-Guidelines>, AHA guidelines website: <http://professional.heart.org/professional/GuidelinesStatements/searchresults.jsp?q=&y=&t=1001>

6. RESTRICTIONS DURING THE STUDY AND CONCOMITANT TREATMENTS

6.1 Restrictions during the study

Contraception

Women of childbearing potential (WOCBP) who are sexually active with a non-sterilized male partner must use at least one highly effective method of contraception (Table 8) from the time of screening and must agree to continue using such precautions for 60 days after the last dose of avelumab. The male partner of a female subject must also use male condom plus spermicide throughout this period. Cessation of birth control after this point should be discussed with a responsible physician. Not engaging in sexual activity is an acceptable practice; however, occasional abstinence, the rhythm method, and the withdrawal method are not acceptable methods of contraception. Female patients should refrain from breastfeeding and egg cell donation throughout this period.

- Females of childbearing potential are defined as those who are not surgically sterile (i.e., bilateral tubal ligation, bilateral oophorectomy, or complete hysterectomy) or postmenopausal (defined as 12 months with no menses without an alternative medical cause).
- Effective methods (including highly effective methods) of contraception are described in Table 8. A highly effective method of contraception is defined as one that results in a low failure rate (i.e., less than 1% per year) when used consistently and correctly. Note that not all methods in Table 8 are considered highly effective.
- Non-sterilized male subjects who are sexually active with a female partner of childbearing potential must use male condom plus spermicide (see Table 8) from screening through 60 days after the last dose of avelumab. Not engaging in sexual activity is an acceptable practice; however, occasional abstinence, the rhythm method, and the withdrawal method are not acceptable methods of contraception. Male patients should refrain from sperm donation throughout this period. Female partners of a male subject must use an effective method of contraception throughout this period.

Table 8: Effective Methods of Contraception

Barrier/Intrauterine Methods	Hormonal Methods

• Male or female condom with or without spermicide ^{a,b,c}• Female cap, diaphragm or sponge with spermicide ^{a,b,c}• Copper T intrauterine device ^e• Levonorgestrel-releasing intrauterine system (eg, Mirena[®]) ^{d,e}	
• Implants^e• Hormone shot or injection^e• Combined pill^e• Minipill^b• Patch^e

^a Female partners of male subjects must use an effective method of birth control

^b Not highly effective (i.e. failure rate of >1% per year)

^c A combination of male condom with either cap, diaphragm or sponge with spermicide (double barrier methods) are also considered acceptable, but not highly effective, birth control methods

^d This is also considered a hormonal method

^e Highly effective (i.e. failure rate of <1% per year)

Blood donation

Subjects should not donate blood while participating in this study, and for at least 60 days following the last infusion of avelumab.

6.2 Excluded concomitant medications or therapies

The following medications are considered exclusionary during the study.

- Any investigational anticancer therapy other than avelumab.
- Any concurrent chemotherapy, radiotherapy, immunotherapy, biologic or hormonal therapy for cancer treatment.
- Growth factors (including G-CSF, GM-CSF, EPO agonists or TPO mimetics)
- Systemic administration of immunosuppressive medications will not be allowed except for those detailed in section 4.2 and those used to manage adverse events as detailed in sections 5.5-5.7 of the protocol.
- Live vaccination within 4 weeks of the first dose of avelumab and while on trial is prohibited. Inactivated vaccines are allowed to be administered.

7. STUDY PROCEDURES

7.1 Study Calendar

Time Points	Pre-study	C1	C2	C3	Pre-surgery ^b	Surgery	Follow-up			End of Study visit	Follow-up
	30 days before D1	D1	D15	D29	D40-50	D41-64	2-3 weeks post-op	30 days post-op	60 days post-op	90 days post-op ^c	To 2 years post-op
Study Assessment											
Signed Informed Consent	X										
Eligibility Criteria	X										
Cancer Staging	X										
Physical Exam with ECOG Performance Status (PS)	X ^a		X	X	X ^b		X	X	X	X ^c	
Medical History/Smoking History/Occupation Hazard	X										
FFPE Tissue for Translational Endpoints^d	X						X				
Laboratory Analysis											
CBC with diff and CMP	X		X	X	X		X	X	X	X	
UPT (if female of CBP)	X			X	X						
Hepatitis B surface antigen, Hepatitis C antibody and HIV 1/2 ELISA	X										
Hepatitis C RNA (if hepatitis C antibody positive)	X										
ACTH, Hemoglobin A1C, and TSH	X				X			X		X	
Free T4 (if TSH abnormal as indicated in Table 7)	X				X			X		X	
Imaging											
CT chest ^e	X				X					X	
CT or MRI abdomen/pelvis ^f	X				X					X	
Treatment											
Avelumab		X	X	X							
Adverse events and their management noted			X	X	X		X	X	X	X ^g	
Radical Cystectomy						X					
Pathology Assessment							X				
DFS Follow-up post-study											X

Footnotes:

- a. Enrollment history and physical.
- b. End of treatment visit.
- c. End of study visit to be performed no earlier than Day 90 after RC.
- d. FFPE tissue from the pre-study time point refers to tissue from the TURBT. FFPE tissue from the 2-3 week post-op time point refers to FFPE tissue from the RC.
- e. Contrast will be used as long as not precluded by creatinine clearance. If a patient is allergic to CT contrast they will be appropriately pre-medicated with steroids +/- antihistamines unless they have a history of anaphylaxis. CT of the chest to be completed in +/- 14 days.
- f. CT with contrast is preferable. However, MRI with contrast or non-contrast CT may be done based on creatinine clearance, allergies, and ability to tolerate contrast. If a patient is allergic to CT contrast, they will be appropriately pre-medicated with steroids +/- antihistamines unless they have a history of anaphylaxis. CT of the abdomen/pelvis to be completed in +/- 14 days.
- g. To be performed at the end of study visit.

Allowable Windows:

1. TURBT should be done within 6 weeks of registration.
2. Avelumab administration should be within +/- 3 days of listed days.
3. Laboratory analysis on day 15 and day 29 may be performed on the day of infusion if results are received prior to avelumab administration. Alternatively, these laboratory analysis may be performed the day prior to avelumab administration.
4. The **end of treatment visit** (post-treatment pre-surgery) should be performed between days 40 and 50.
5. The **end of study visit** should be 90 days after surgery +/- 10 days.
6. On-treatment visits with history and physical exam should be ≤ 3 days before a scheduled dose of avelumab.
7. RC may be done any time after the pre-surgery evaluation is completed, but no later than day 64.
8. History and physical exams performed after RC (with the exception of the end of study visit) have a time window of +/- 7 days.
9. Post-operative labs up to day 60 after RC have a time window of +/- 7 days.

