7.2.5 Follow-up schedule

- Any patient receiving ≥ 1 dose of avelumab will be followed up to 90 days after RC (or end of last cycle of avelumab for those not receiving RC) to evaluate for safety. The indicated follow-up is outlined in the study calendar.
- Those patients evaluable for secondary endpoints will be followed up on study to day 90 after RC as outlined in the study calendar.
- After the safety monitoring period of 90 days post RC those patients who are evaluable for secondary endpoints will be followed off study for recurrence and survival for up to 2 years after RC. This may be done by physician visits/imaging performed approximately every 3 months for those undergoing surveillance at Baylor affiliates or by phone conversations approximately every 3 months for those undergoing surveillance at practices outside of Baylor affiliates.

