9.8 Study recording period and follow-up for adverse events

AEs and SAEs will be recorded from the time of first treatment with Avelumab, throughout the treatment period and including the follow-up period (90 days after RC). During the course of the study all AEs and SAEs will be proactively followed up for each subject. Every effort will be made to obtain a resolution for all events, even if the events continue after discontinuation/study completion.

If a subject discontinues treatment for reasons other than disease progression, and therefore continues to have tumor assessments, drug or procedure-related SAEs must be captured until

the patient is considered to have confirmed PD and will have no further tumor assessments. The investigator is responsible for following all SAEs until resolution, until the subject returns to baseline status, or until the condition has stabilized with the expectation that it will remain chronic, even if this extends beyond study participation.

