9.9 Follow-up of unresolved events

Any AEs that are unresolved at the subject's last visit in the study are followed up by the investigator for as long as medically indicated, but without further recording in the adverse event log. After 90 days post-RC, only subjects with ongoing investigational product-related SAEs will continue to be followed for safety.

Pfizer retains the right to request additional information for any subject with ongoing AE(s)/SAE(s) at the end of the study, if judged necessary.

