12.3 Study timetable and end of study

The end of the study will be defined as the time point 90 days after RC. The recruitment period is estimated to take place over a period of approximately 12 months.

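### Two rules in the study calendar disagree on the earliest day for the end-of-study visit: day 90 after cystectomy (footnote c) or day 80 (allowable window 5)

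*Protocol*

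**What the plan says.** Protocol section 7.1 (Study Calendar) times the end-of-study visit twice. Footnote c: "End of study visit to be performed no earlier than Day 90 after RC". Item 5 of the allowable windows: the visit "should be 90 days after surgery +/- 10 days". Item 8 gives the other post-operative examinations a tolerance of 7 days either way and expressly leaves this visit out, so footnote c and item 5 are the only rules that govern it.

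Footnote g, attached to the last AE entry in the calendar, reads "To be performed at the end of study visit". The only item scheduled after that visit is follow-up for disease-free survival (DFS). Section 7.2.5 describes that follow-up as off study: patients "will be followed off study for recurrence and survival for up to 2 years after RC".

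The length of the safety period is stated consistently elsewhere:

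- Section 7.2.5: treated patients "will be followed up to 90 days after RC (or end of last cycle of avelumab for those not receiving RC) to evaluate for safety".
- Section 9.8: AEs and serious AEs (SAEs) are recorded "throughout the treatment period and including the follow-up period (90 days after RC").
- Section 9.12: death reporting uses a 90-day period after RC.
- Section 12.3: "The end of the study will be defined as the time point 90 days after RC".

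Section 9.9 adds that AEs unresolved at a patient's last study visit are followed for as long as medically needed, "but without further recording in the adverse event log".

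**The concern.** Both rules use the same anchor (surgery) and concern the same visit, and nothing in the protocol says which prevails. A coordinator working from the list of windows could book the visit on day 82 in good faith. The patient would then have a protocol deviation under footnote c and none under item 5.

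The second issue is safety information. Safety in the neoadjuvant setting is a secondary objective (section 2.2), and the target is only 10 evaluable patients (section 3.1). If the last scheduled AE review falls before day 90, the rest of the safety period has no planned contact. For an event still open at that visit, sections 9.8 and 9.9 also give different end dates for logging: day 90 under 9.8, the date of the visit under 9.9.

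**Working it through.** The check is interval arithmetic in days after RC. All inputs come from section 7.1, except the recording period (section 9.8).

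**1. The two rules**

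- Window 5: 90 - 10 = day 80 to 90 + 10 = day 100, which is 100 - 80 + 1 = 21 calendar days.
- Footnote c: day 90 or later, with no upper limit.

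**2. Overlap and conflict**

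- Both rules met: days 90 to 100, or 11 days.
- Window 5 met, footnote c broken: days 80 to 89, or 10 days.
- Share of window 5 in conflict: 10/21 = 48%.

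**3. Safety time after the last scheduled assessment**

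- The recording period ends on day 90. After a visit on day 80, 90 - 80 = 10 days remain. This is the maximum; a visit on day 89 leaves 1 day.
- Share of the post-operative safety period: 10/90 = 11.1%.
- Share of the whole AE period from the first dose, with RC on study days 41 to 64 as in the calendar:
  - RC on day 41: 40 + 90 = 130 days; 10/130 = 7.7%.
  - RC on day 64: 63 + 90 = 153 days; 10/153 = 6.5%.

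**4. Which rule fits the rest of the protocol**

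| Provision | Point in time after RC |
|---|---|
| 7.1, footnote c | day 90 or later |
| 7.1, window 5 | days 80 to 100 |
| 7.2.5, safety follow-up | to 90 days |
| 9.8, AE and SAE recording | to 90 days |
| 9.12, death reporting | 90-day period |
| 12.3, end of study | 90 days |

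Footnote c guarantees that the final visit does not come before the safety period ends. The lower half of window 5 is the only provision that lets it do so.

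**5. What is not affected**

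The safety set needs only one dose of avelumab (section 3.4), so its denominator does not depend on the visit date. The primary endpoint uses tissue from the transurethral resection and from RC, so it is complete well before this visit. As a side check, a paired t-test with 10 patients, correlation 0.5, a change of 1 standard deviation and two-sided alpha of 5% has power 0.803. That reproduces the roughly 80% in section 10.1, and the visit window plays no part in it. Any effect on 2-year DFS is negligible.

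**The case against.** The strongest reply is that the gap appears only if a site ignores footnote c. Footnote c is worded as a prohibition and window 5 as a recommendation, and a site that honours both will see patients on days 90 to 100 and lose nothing. This limits the consequence but does not remove the conflict: on that reading the minus 10 has no meaning, and no text tells a site to prefer the stricter rule.

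It is also true that recording is not shortened. Section 9.8 still requires AEs and SAEs to be captured and proactively followed to day 90, section 9.12 still requires deaths in that period to be reported, and section 9.10 lifts active reporting only afterwards. What is lost is a scheduled assessment, not the duty to record.

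The percentages above are shares of calendar time, not of missed events. Visits at 30, 60 and 90 days already leave about 30 days between assessments, so the real difference is that no later on-study visit would pick up a late onset. Exposure matters too. With the third dose on day 29 and RC on days 41 to 64, a visit 80 days after RC falls 41 + 80 - 29 = 92 to 64 + 80 - 29 = 115 days after the last nominal dose, so the practical loss for drug safety is modest.

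Two smaller points stand. The protocol gives the day-90 laboratory tests no window of their own (item 9 stops at day 60), so it is an inference that they would move with an early visit. And the conflict between 9.8 and 9.9 disappears for this visit once it cannot precede day 90, so an edit to 9.9 is secondary.

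**Conclusion.** The concern holds. Footnote c and window 5 contradict each other on days 80 to 89 after RC, which is 10 of the 21 days that window 5 allows, and the minus 10 in window 5 is the part that does not fit the rest of the protocol. At worst, 10 of the 90 post-operative safety days pass without a scheduled AE assessment, and the end date for logging an open event becomes ambiguous.

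The 10-day figure assumes that a site follows window 5 to its lower limit. The shares of the whole AE period assume RC on the calendar's nominal days 41 to 64. How many patients would be seen early, and how many events would be affected, cannot be derived from the protocol. This is a minor inconsistency worth correcting; it does not threaten any of the trial's conclusions.

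**What to change.** Change item 5 of the allowable windows in section 7.1 to 90 days after surgery, -0/+10 days (days 90 to 100). This satisfies both rules and reduces the uncovered safety time from at most 10 days to none.

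As an optional clarification, state in section 9.9 that unresolved events stay in the AE log through day 90 after RC even if a patient's last visit comes earlier. With the new window this matters only for patients whose last visit is early for some other reason.

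If the sponsor wants to keep the option of an early visit, the alternative is to delete footnote c and add an AE contact at day 90.

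The preferred change takes one line of amendment, or two with the clarification. The cost is a window of 11 days instead of 21, which footnote c already imposes.
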